7.2 Treatment Period

All patients will receive 200 mg of pembrolizumab Q3W for up to 2 years from Day 1.

In Phase 1 Dose Escalation, patients in Escalation Cohorts 1-4 will receive SD-101 from Day 1 through Day 169 (Figure 4-2).

In Phase 2 Dose Expansion, patients naïve to anti-PD-1/L1 in Cohorts 1 and 3 will receive SD-101 from Day 22 through Day 421 (Figure 4-3) and patients experienced with anti-PD-1/L1 in Cohorts 2 and 4 will receive SD-101 from Day 1 through Day 400 (Figure 4-4). Patients in Cohorts 5, 6, 7, and 8 will receive SD-101 from Day 1 through Day 358 (Figure 4-5).

Pembrolizumab will be continued until completion of planned dosing (up to 2 years) or required discontinuation as described in Section 7.6. SD-101 will be continued until completion of planned dosing, confirmed disease progression, or required discontinuation as described in Section 9.2 (whichever occurs sooner).

Details of the dosing for Phase 1 and Phase 2 are provided in the Schedule of Trial Events (Appendix 1 through Appendix 4).

SD-101 will be administered before pembrolizumab on days when both drugs are scheduled to be used.

Note: If pembrolizumab treatment is temporarily withheld, treatment of SD-101 and pembrolizumab will start on the same day once pembrolizumab is resumed. Delayed dosing of SD-101 would be preferred over completely skipping a dose as long as the interval between SD-101 dosing is not less than 5 days with subsequent return of SD-101 dosing to per protocol schedule of events. See Section 7.6 for details regarding delayed or skipped doses.

The protocol may be discontinued by Dynavax Technologies Corporation at any time (Section 4.7).

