7.6 Dose Modification, Dose Delays, and Missed Doses

NOTE: As of Amendment 9, irRECIST for the determination of disease progression is no longer applicable and this section has been revised accordingly.

Only a limited number of patients have been treated with SD-101, and to date, the most common toxicities include transient Grade 1 to 2 flu-like symptoms. In mice, SD-101 has been injected intratumorally concurrently with a neutralizing anti-mouse PD-1 antibody. In multiple experiments using high doses of SD-101 (approximately 2 mg/kg), no evidence of acute morbidity or mortality in mice was observed that could be due to the interaction of the 2 agents.

To protect patient safety, patients will be closely monitored for any additional or synergistic toxicities observed with the combination.

Withhold SD-101 for any Grade ≥ 3 injection-site reaction or drug-related AE that is not a DLT (see Section 9.1). SD-101 treatment may be resumed once the AE has resolved to Grade 0 or 1 with standard treatment. SD-101 must also be held for an ANC count of < 1500 cells/mcL.

Patients will be treated at the dose in their assigned Cohort and individual dose adjustment (reduction or increase) of SD-101 or pembrolizumab will not be permitted.

Delayed dosing of SD-101 would be preferred over completely skipping a dose as long as the interval between SD-101 dosing is not less than 5 days with subsequent return of SD-101 dosing to per protocol schedule of events. If the 5-day interval cannot be adhered to, then the injection must be skipped to allow a minimum of 5-day interval window between the off-scheduled injection and next injection on schedule. After a delayed or skipped dose, dosing will return to the original interval as described under Schedule of Trial Events.

For Phase 1, if ≥ 2 doses are missed during the DLT assessment period for any reason or if ≥ 4 doses are missed due to AEs following the DLT period, then SD-101 should be permanently discontinued. For Phase 2, if ≥ 4 doses are missed due to AEs, then SD-101 should be permanently discontinued.

If SD-101 dosing is delayed for more than 3 days, then the hematology and chemistry laboratory collections listed in the Schedule of Trial Events ([Appendix 1](#) through [Appendix 4](#)) or the planned day of dosing that were missed should be done prior to dosing on that day (eg, if Day 22 dosing is delayed and SD-101 is dosed on Day 26, then all the Day 22 labs should be repeated pre-dose on Day 26).

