SD-101 should be withheld if a patient requires greater than 10 mg per day of prednisone or equivalent to treat an AE (Section 9.3.2). SD-101 may be resumed when the corticosteroid is discontinued and pembrolizumab is resumed.

If an HNSCC subject develops an AE which requires anticoagulation therapy, the Investigator in consultation with the Medical Monitor will determine whether SD-101 injection should be continued or interrupted.

SD-101 should be permanently discontinued for any of the following:

- SD-101 dosing is delayed for more than 6 weeks
- DLT that occurs during the DLT assessment period in Phase 1 (Section 9.1)

- Clinically significant immune-related event
- Pembrolizumab is permanently discontinued

SD-101 will be permanently discontinued for any of the following adverse reactions (ARs):

- Severe or life-threatening ARs, including any of the following:
 - Any Grade 4 (life-threatening) AR
 - Grade 3 or 4 pneumonitis
 - Grade 4 diarrhea/colitis
 - Grade 4 hyperthyroidism
 - Grade 3 AST or ALT of $> 5 \times \text{ULN}$ or Grade 3 total serum bilirubin $> 3 \times \text{ULN}$
 - AST or ALT increases by greater than or equal to 50% relative to baseline and lasts for at least 1 week in patients with liver metastasis who begin treatment with a baseline Grade 2 AST or ALT of > 3 and $\leq 5 \times \text{ULN}$
 - Grade 3 or 4 nephritis
 - Any severe or Grade 3 AR that recurs
 - Inability to reduce corticosteroid dose (used for treatment of AEs) to 10 mg or less of prednisone or equivalent per day within 12 weeks of starting corticosteroids
- Observation of any other toxicities that in the opinion of the investigators suggests that there may be a significant increase in either the incidence or severity of any events seen with either single agent. In this case, the sponsor and investigators will review all safety data.

Pembrolizumab must be withheld for drug-related toxicities and severe or life-threatening AEs as listed in [Table 7-1](#). If a patient's AE prevents pembrolizumab dosing then SD-101 injection should be held if the AE also could at least be possibly related to SD-101. Delayed dosing of SD-101 would be preferred over completely skipping a dose as long as the interval between SD-101 dosing is not less than 5 days with subsequent return of SD-101 dosing to per protocol schedule of events. See [Section 7.7](#) for use of corticosteroids.

Grade 2 - 3 fatigue does not require the withholding of pembrolizumab or SD-101 treatment.

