AST / ALT elevation or Increased bilirubin	Grade 2	Withhold	Administer corticosteroids (initial dose of 0.5- 1 mg/kg prednisone or equivalent) followed by taper	Monitor with liver function tests (consider weekly or more frequently until liver enzyme value returned to baseline or is stable)
	Grade 3 or 4	Permanently discontinue	Administer corticosteroids (initial dose of 1-2 mg/kg prednisone or equivalent) followed by taper	
T1DM or Hyperglycemia	Newly onset T1DM or Grade 3 or 4 hyperglycemia associated with evidence of β -cell failure	Withhold	Initiate insulin replacement therapy for participants with T1DM Administer anti-hyperglycemic in participants with hyperglycemia	Monitor participants for hyperglycemia or other signs and symptoms of diabetes.

Table 7-1: Dose Modification and Toxicity Management Guidelines for Immune-related Adverse Events Associated with Pembrolizumab (Cont'd)

Immune-related AEs	Toxicity grade or conditions (CTCAEv4.0)	Action taken to pembrolizumab	irAE management with corticosteroid and/or other therapies	Monitor and follow-up
Hypophysitis	Grade 2	Withhold	Administer corticosteroids and initiate hormonal replacements as clinically indicated.	Monitor for signs and symptoms of hypophysitis (including hypopituitarism and adrenal insufficiency)
	Grade 3 or 4	Withhold or permanently discontinue		
Hyperthyroidism	Grade 2	Continue	Treat with non-selective beta-blockers (e.g., propranolol) or thionamides as appropriate	Monitor for signs and symptoms of thyroid disorders.
	Grade 3 or 4	Withhold or permanently discontinue		
Hypothyroidism	Grade 2-4	Continue	Initiate thyroid replacement hormones (eg, levothyroxine or liothyronine) per standard of care	Monitor for signs and symptoms of thyroid disorders.
Nephritis and Renal dysfunction	Grade 2	Withhold	Administer corticosteroids (prednisone 1-2 mg/kg or equivalent) followed by taper.	Monitor changes of renal function
	Grade 3 or 4	Permanently discontinue		
Myocarditis	Grade 1 or 2	Withhold	Based on severity of AE administer corticosteroids (prednisone 1-2 mg/kg or equivalent) followed by taper.	Ensure adequate evaluation to confirm etiology and/or exclude other causes
	Grade 3 or 4	Permanently discontinue		

Table 7-1: Dose Modification and Toxicity Management Guidelines for Immune-related Adverse Events Associated with Pembrolizumab (Cont'd)

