If pembrolizumab treatment is temporarily withheld, treatment of SD-101 and pembrolizumab will start on the same day once pembrolizumab is resumed. Delayed dosing of SD-101 would be preferred over completely skipping a dose as long as the interval between SD-101 dosing is not less than 5 days with subsequent return of SD-101 dosing to per protocol schedule of events (see Section 7.6 for details regarding delayed or skipped doses). If both study drugs are on hold, the study visit(s) during the hold period may be skipped, with the exception that radiographic imaging must be performed according to schedule.

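### When an immune-related event withholds pembrolizumab, the protocol's SD-101 rules conflict on whether to hold, restart or permanently stop it, so patients with the same event can be handled differently

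*Protocol*

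**What the plan says.** Four sets of protocol text apply to SD-101 when pembrolizumab is withheld.

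- **Hold by attribution.** Section 7.6: when an adverse event prevents pembrolizumab dosing, "SD-101 injection should be held if the AE also could at least be possibly related to SD-101". It does not say what happens otherwise.
- **Joint restart.** Section 7.2: "If pembrolizumab treatment is temporarily withheld, treatment of SD-101 and pembrolizumab will start on the same day once pembrolizumab is resumed". Sections 9.2 and 10.2 repeat this. None of the three adds an attribution condition. Section 10.2 goes on: "If both study drugs are on hold, the study visit(s) during the hold period may be skipped".
- **Permanent stop.** Section 7.6: "SD-101 should be permanently discontinued for any of the following", and one item is "Clinically significant immune-related event". The next list in the same section gives grades, for example "Grade 3 or 4 pneumonitis" and Grade 4 diarrhea/colitis. Earlier in Section 7.6, after a hold for a Grade 3 or higher drug-related event that is not a DLT, "SD-101 treatment may be resumed once the AE has resolved to Grade 0 or 1 with standard treatment".
- **Time limits.** Section 7.6 ends SD-101 after a delay of more than 6 weeks. Table 7-1 ends pembrolizumab if the event has not resolved within 12 weeks of the last dose.

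Section 7.6 also withholds SD-101, regardless of attribution, while more than 10 mg/day of prednisone or equivalent is needed. It lets SD-101 resume once the steroid is stopped and pembrolizumab is back.

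**The concern.** One trigger, a pembrolizumab hold for an immune-related event, leads to different SD-101 actions depending on which sentence a site applies. The rules are still in use: under Amendment 9 enrollment is closed, but Section 4.1.2 keeps enrolled Phase 2 patients on their assigned treatment.

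Two things are at stake. The first is consistent handling of a patient with active immune toxicity. The second is the safety summary: SAP Section 9.7.3 tabulates treatment-emergent events leading to study drug discontinuation, and both that table and SD-101 exposure would partly reflect the rule a site followed rather than the toxicity itself.

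**Working it through.** The plan gives no figure to reproduce here. The check compares the rules on three Table 7-1 events and then does arithmetic on the time limits.

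**Case 1: Grade 2 pneumonitis.** Table 7-1 withholds pembrolizumab and gives prednisone at 1–2 mg/kg. Even the lowest mg/kg starting dose in the table, 0.5 mg/kg, exceeds 10 mg/day above 10 / 0.5 = 20 kg body weight. The steroid rule therefore holds SD-101 whatever the attribution, and continuing is closed. What remains open is hold and restart, or permanent stop if the event is judged clinically significant. The graded list names pneumonitis only from Grade 3.

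**Case 2: Grade 3 diarrhea/colitis.** Pembrolizumab is withheld and steroids are given, so SD-101 is held. The graded entry stops SD-101 at Grade 4; the ungraded bullet could stop it at Grade 3. Section 7.6 elsewhere foresees resuming after a Grade 3 drug-related event.

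**Case 3: new-onset type 1 diabetes, judged not even possibly related to SD-101.** The Table 7-1 row begins "Newly onset T1DM or Grade 3 or 4 hyperglycemia associated with evidence of" β-cell failure. Pembrolizumab is withheld and insulin started; no steroid is listed, so the steroid rule is not triggered.

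- The attribution sentence in Section 7.6 gives no reason to hold SD-101, which implies that injections go on.
- Sections 7.2, 9.2 and 10.2 have both drugs start together when pembrolizumab resumes, which implies that SD-101 was held.
- The ungraded bullet, if applied, ends SD-101.

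The Section 7.6 hold for Grade 3 or higher events says drug-related, not SD-101-related, and Section 6.0 calls both agents trial drugs. If pembrolizumab counts, Grade 3–4 hyperglycemia also holds SD-101, and the three-way case shrinks to events below Grade 3.

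**Time limits.** Put the last pembrolizumab dose at week 0, with dosing every 3 weeks and the hold starting at the first missed dose.

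- First missed dose: week 3. The pembrolizumab limit is week 12, which is 12 − 3 = 9 weeks after the first missed dose.
- If SD-101 is held from the same visit, its delay passes 6 weeks after week 3 + 6 = 9.
- For SD-101 delays of more than 6 and up to about 9 weeks, pembrolizumab may still resume. The joint-restart sentence and the permanent stop then both apply.
- With steroids: if the event takes t weeks from the first missed dose to reach Grade 1 or less, and the Table 7-1 taper lasts at least 4 weeks, the SD-101 delay is at least t + 4 weeks. It exceeds 6 weeks once t > 2.

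**Largest exposure difference within the pembrolizumab limit.** In the every-3-week part of the SD-101 schedule, the visits before week 12 fall at weeks 3, 6 and 9. That is 3 visits: 3 × 8.0 mg = 24 mg at the highest per-visit dose, or 3 × 2.0 mg = 6 mg for a one-lesion patient in Cohorts 5 to 7.

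**The case against.** The strongest reply is that the text can be harmonised. The same-day sentence may govern restart only when both drugs were held; Section 10.2 supports this by treating a joint hold as one possibility. The two time limits belong to different drugs, and Section 9.2 lets pembrolizumab continue alone after SD-101 stops. The ungraded bullet may be meant only for serious events. The graded list is not exhaustive either: it also covers any Grade 4 adverse reaction, a recurring Grade 3 reaction, and other toxicities that worry the investigators. These readings are coherent, but no section states them. The same-day sentence appears three times with no carve-out for attribution or for the 6-week stop.

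Four stronger readings are tempting, and the documents do not support them.

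- A reader might infer that the protocol tells sites to continue SD-101. It does not; continuing is only implied by a conditional sentence.
- A reader might extend the three-way conflict to every Table 7-1 row that withholds pembrolizumab. The steroid rule closes the continue branch wherever prednisone is given at mg/kg doses.
- A reader might count a full 12-week hold as 4 visits and 32 mg. The limit runs from the last dose, so the fourth visit falls on the limit itself. For diabetes the hold may be shorter: the note under Table 7-1 lets pembrolizumab resume after a Grade 3–4 endocrinopathy once it is Grade 2 or less and controlled.
- A reader might see these rules as the main safeguard left after Amendment 9. Section 9.0 leaves discontinuation to the investigator under local standard of care, Section 9.2 keeps unacceptable adverse events and patient best interest as stopping grounds, and AE and SAE reporting continues.

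Investigator discretion does not remove the conflict. The Section 8.2 note requires discontinuation decisions to follow Section 9.2, which points back to Section 7.6, and the discretion note under Table 7-1 covers pembrolizumab only.

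**Conclusion.** The conflict is real but bounded. The SD-101 hold depends on attribution in Section 7.6, whereas the same-day restart in Sections 7.2, 9.2 and 10.2 does not. The ungraded permanent-stop bullet sits beside graded thresholds and a resume rule. The 6-week and 12-week limits leave a window of more than 6 to about 9 weeks of SD-101 delay in which restart and permanent stop both apply.

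Hold versus permanent stop can arise for withheld events generally. The three-way conflict needs an event managed without more than 10 mg/day prednisone and judged not even possibly related to SD-101, and it is narrower still if drug-related includes pembrolizumab. The exposure difference is at most about 3 visits, or 24 mg, before the pembrolizumab limit, assuming every-3-week dosing and a hold from the first missed dose. A permanent stop would also remove every later SD-101 dose.

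Frequency cannot be estimated. The number of patients still on SD-101 is not given. The Phase 1 experience in Section 2.6 was 2 immune-related events in 22 patients (9%), one pneumonitis and one hypophysitis, neither of them diabetes. Patients can therefore be handled differently; the documents do not show that any were. The effect on results is confined to descriptive safety and exposure summaries. The reason to act is that contradictory toxicity instructions apply to patients on treatment.

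**What to change.** Reconcile Sections 7.2, 7.6, 9.2 and 10.2 into one SD-101 instruction for a pembrolizumab hold, and in it:

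1. State whether attribution to SD-101 matters, and what happens when the event is judged unrelated to it.
2. State whether drug-related, in the Grade 3 or higher hold, includes pembrolizumab.
3. Define the ungraded immune-related bullet by event and grade, or delete it if the graded list governs.
4. State how the 6-week SD-101 limit and the 12-week pembrolizumab limit apply together, including whether the 6-week stop overrides the joint restart.

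Which rule stands is for the sponsor to decide. The cost is a short clarification letter or amendment text, with no new data or procedures.

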7.8 Replacement of Patients

NOTE: As of Amendment 9, enrollment is closed and this section is no longer applicable.

Patients who complete screening but are not treated or patients who do not complete at least 3 injections of SD-101 during the DLT assessment period for reasons other than drug-related toxicity will be replaced. Patients who withdraw from the trial during the DLT assessment interval prior to Day 29 for reasons other than a drug-related toxicity may be replaced.

Patients who received < 90% of pembrolizumab during the DLT assessment period (eg, because the infusion had to be discontinued due to an infusion reaction) and did not experience a DLT will not be taken into account in the assessment of the overall DLT rate for the particular dose level cohort and will be replaced.

Phase 2 patients who do not receive the following may be replaced at the decision of the Dynavax Medical Monitor:

- At least 1 dose of SD-101 and pembrolizumab
- Baseline and at least 1 post-baseline imaging
- Baseline and at least 1 post-baseline tumor biopsy

8.0 ASSESSMENT OF RESPONSE

NOTE: As of Amendment 9, efficacy and exploratory endpoints will no longer be collected. The collection of safety endpoints has been simplified. Assessments of disease response to treatment should be made per Investigator based on local standard of care.

Response assessments will be performed at specified time points as listed in the Schedule of Trial Events ([Appendix 1](#) through [Appendix 4](#)).

8.1 Interferon-inducible Genes

NOTE: As of Amendment 9, this section is no longer applicable.

IFN-inducible gene expression will be measured in Phase 1 to indirectly determine the induction of IFN- α by different doses of SD-101. In addition to DLT assessment, the levels of IFN-inducible gene expression may be used to determine the optimal RP2D of SD-101 for further evaluation of combination therapy in oncology trials. The rationale for utilizing IFN-inducible gene expression as a factor in choosing an optimal dose of SD-101 is to ensure that an appropriately active dose of SD-101 will be used since preclinical data have suggested that high doses of CpGs may paradoxically lower CpG stimulated immune response due to a

compensatory mechanism of the immune system. Induction of IFN- α responsive genes is considered a surrogate for the activity of SD-101 since engagement of TLR9, the target of SD-101, indirectly resulting in an upregulation of these genes. Specifically, fold increases in IFN-inducible genes will be analyzed per individual gene and as a combination of genes on a cohort basis to provide assurances that an appropriately active dose of SD-101 will be used.

IFN-inducible gene expression may also be measured in up to 12 patients in each of the Phase 2 Expansion HNSCC cohorts to understand HNSCC tumor responses.

8.2 Response Evaluation and Criteria

NOTE: As of Amendment 9, Section 8.2 and its subsections (8.2.1, 8.2.1.1, and 8.2.1.2) are no longer applicable. All disease response assessments, including the timing, type, and evaluation of imaging, are to be performed and assessed per the Investigator based on local standard of care; the data will not be collected and no longer need to be recorded in the CRF. Confirmation of progression by repeat imaging is not mandatory. Decisions on treatment discontinuation should be made per Investigator based on local standard of care and in accordance with the stopping rules outlined in Section 9.2. The text in these sections is retained as a reference only to aid Investigators in making treatment decisions and is not mandatory.

All baseline efficacy evaluations will be performed at Screening. Baseline radiographic and superficial measurement (as applicable for superficial lesions) must be performed no more than 4 weeks prior to study enrollment. The same imaging method used at baseline should be used throughout the study unless a change is required due to AEs (eg, new radiographic contrast allergy) per local radiology guidelines.

Evaluation of superficial lesions requires both photographic and manual (caliper) measurement at all time points that radiographic imaging is required per Schedule of Trial Events ([Appendix 1](#) through [Appendix 4](#)). Although radiographic imaging collected at the scheduled time points is preferred, it is allowed to be obtained the day prior to study treatment.

Response to treatment and disease progression will be evaluated by the investigator and recorded on the CRF every 9 weeks after the first trial injection until Day 379 and then every 12 weeks thereafter for the remainder of the trial. All treatment response and disease progression require confirmation of response (complete response [CR] or partial response [PR]) using RECIST v1.1 and irRECIST, which is the study-specific irRECIST that requires confirmation of disease progression with an additional scan obtained at least 4 weeks later that also meets the criteria of PD per RECIST v1.1 ([Appendix 6](#), Immune-related RECIST). Patients with suspected disease progression should continue to follow trial procedures until they have confirmed disease

progression. It is at the discretion of the investigator whether to continue a patient on study treatment until repeat imaging is obtained (per irRECIST patient management). This clinical judgment decision by the investigator should be based on the patient's overall clinical stability defined as the following:

- 1) Absence of symptoms and signs indicating clinically significant progression of disease, including worsening of laboratory values
- 2) No decline in ECOG PS
- 3) Absence of rapid progression of disease
- 4) Absence of progressive tumor at critical anatomical sites (eg, cord compression) requiring urgent alternative medical intervention

If repeat imaging confirms PD due to any of the scenarios listed in [Appendix 6](#), Immune-related RECIST, patients will be discontinued from study therapy. If repeat imaging does not confirm PD by irRECIST and the patient continues to be clinically stable, treatment may continue and follow the regular radiographic imaging schedule. If a patient requires another anti-cancer therapy, radiographic imaging and measurement of superficial lesions will be discontinued.

Please refer to Section [10.8](#) for EOS visit and procedures regarding discontinuation from the trial.

